7. Archival tissue [paraffin block(s) or unstained slides from paraffin block(s)] from the primary tumor and/or a metastatic site judged reasonably available prior to initiating treatment, or willingness to undergo fresh pre-treatment tumor biopsy. Prior to initiating treatment, the screening team must have documentation that a paraffin block(s), unstained slides from a paraffin block(s), or a fresh biopsy has been requested from a local or outside facility. (However, physical possession of requested tissue, or waiting for histological analysis or confirmation that a certain number of acquired specimen slides are known to contain tumor tissue, is not a requirement prior to initiating treatment.) Please note: Archival or fresh biopsy should be excisional, incisional or core needle; fine needle aspiration is not sufficient. Patients without available or sufficient archival tumor samples (if otherwise eligible) will be allowed to participate, if they are willing to have a fresh biopsy of a primary or metastatic lesion. If no archival tissue is available and patient consents to a fresh biopsy, but the patient's lesion is deemed inaccessible to safe biopsy, the patient will be allowed to enroll if otherwise eligible.
8. In addition to the mandatory archival tissue or fresh tissue, an optional fresh biopsy will be requested from consenting subjects (including those with pre-existing archival tissue) with primary or metastatic lesion judged amenable to medically safe excisional, incisional or core needle biopsy.
9. On Cycle 1, Day 1: Physical exam (including ECOG performance status) and review of Con Meds and Adverse Events not required if already completed within 7 days prior to first dose of avelumab. After initiation of Cycle 4, physical exams may be performed monthly (i.e. after Cycle 4, Day 1 exam to confirm satisfactory completion of Cycle 3, the next regularly scheduled physical exam may occur 4 weeks later, on Cycle 6, Day 1; with subsequent monthly physical exams intended every even cycle, on Day 1 of Cycles 8, 10, 12, etc).
10. Hematology and blood chemistry must be collected prior to each avelumab dose, at the end of treatment visit, and at 30 days post-treatment safety follow-up.
11. Pharmacogenetic (PG) blood obtained once, prior to patient's first avelumab dose on Cycle 1, Day 1.

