7.2. Screening Visit Assessments

Prior to performing any study-based procedures, patient informed consent must be obtained.

The following procedures must be completed ≤ 28 days prior to a patient's first dose of study treatment:

- Signed Informed Consent Form
- Medical history and Demographics
- Physical exam
- Vital signs: heart rate, blood pressure and temperature (oral or tympanic)
- Height
- Weight
- ECOG Performance Status
- Concomitant medications (taken up to 28 days prior to Day 1) and Adverse Events
- Complete Blood Count (CBC) with differential
- Serum chemistry, including Free T4 and thyroid stimulating hormone (TSH)
- Serum Pregnancy test in women of childbearing potential (as defined in Sections 7.1 and 8.6)
- Hepatitis B Virus (HBV) and Hepatitis C Virus (HCV) testing
- Extent of disease evaluation (by CT or MRI scan of the chest, abdomen and pelvis), within 28 days of study treatment
- Archival tumor tissue requested and/or fresh biopsy of lesion amenable to safe biopsy (see Sections 7.1 and 8.7 for additional detail).

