8.7. Archival and Optional Fresh Tumor Samples

Pre-treatment archival tissue [paraffin block(s) or unstained slides from paraffin block(s)] from the primary tumor and/or a metastatic site must be judged to be reasonably available prior to initiating treatment, or the patient must be willing to undergo a fresh pre-treatment tumor biopsy. Prior to initiating treatment, the screening team must have documentation that a paraffin block(s), unstained slides from a paraffin block(s), or a fresh biopsy has been requested from a local or outside facility. (However, physical possession of requested tissue, or waiting for histological analysis or confirmation that a certain number of acquired specimen slides are known to contain tumor tissue, is not a requirement prior to initiating treatment.) Please note: Archival or fresh biopsy should be excisional, incisional or core needle; fine needle aspiration is not sufficient.

Patients (including those with pre-existing archival tissue) may elect to have an optional fresh biopsy of a primary or metastatic lesion judged amenable to medically safe excisional, incisional or core needle biopsy.

Archival tumor samples obtained at the time of metastasis are preferred over tumor samples obtained at the time of primary diagnosis. Approximately 50 total microns of tumor sample (i.e. about 10 slides of 5 microns each) is desired for this purpose – see lab manual for additional details.

In cases where both archival and optional fresh tumor biopsy tissue are available, both archival and fresh samples will be requested.

Patients without available or sufficient archival tumor samples (if otherwise eligible) will be allowed to participate, if they are willing to have a fresh biopsy of a primary or metastatic lesion. If no

archival tissue is available and patient consents to a fresh biopsy, but the patient's lesion is deemed inaccessible to safe biopsy, the patient will be allowed to enroll if otherwise eligible.

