14.1. General

Safety assessments will consist of monitoring and reporting AEs and SAEs that are considered possibly, probably or definitely related to avelumab, all events of death, and any study-specific issue of concern.

Adverse event collection and reporting is a routine part of every clinical trial. Each adverse event will be graded according to the NCI's Common Terminology Criteria for Adverse Events (NCI CTCAE), Version 4.03, dated June 14, 2010, currently locatable via the following URL:

< http://evs.nci.nih.gov/ftp1/CTCAE/CTCAE_4.03_2010-06-14_QuickReference_8.5x11.pdf >.

For events not listed in the CTCAE, severity will be designated as mild, moderate, severe or life threatening, or fatal which respectively correspond to Grades 1, 2, 3, 4, and 5 on the NCI CTCAE, with the following definitions:

- **Mild:** An event not resulting in disability or incapacity and which resolves without intervention;
- **Moderate:** An event not resulting in disability or incapacity but which requires intervention;
- **Severe:** An event resulting in temporary disability or incapacity and which requires intervention;
- **Life-threatening:** An event in which the patient was at risk of death at the time of the event;
- **Fatal:** An event that results in the death of the patient.

Information on all adverse events, whether serious or not, whether reported by the participant, directly observed, or detected by physical examination, laboratory test or other means, will be collected, recorded, followed and reported as described in the following sections.

Reporting period: Adverse events experienced by participants will be collected and reported from initiation of study medication, throughout the study, and within 30 days of the last dose of study medication. Participants who experience an ongoing adverse event related to a study procedure and/or study medication beyond 30 days will continue to be contacted by a member of the study team until the event is resolved, stabilized, or determined to be irreversible by the participating investigator.

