14.3. Safety Parameters and Definitions

14.3.1 Adverse Event (AE)

An AE is any unfavorable and unintended sign, symptom, or disease temporally associated with the use of an investigational medicinal product (IMP) or other protocol-imposed intervention, regardless of attribution. Progressive disease will not be considered an adverse event.

An adverse event includes the following:

- AEs not previously observed in the patient that emerge during the protocol-specified AE reporting period, including signs or symptoms that were not present prior to the AE reporting period.
- Complications that occur as a result of protocol-mandated interventions (e.g. invasive procedures such as biopsy).
- If applicable, AEs that occur prior to assignment of study treatment associated with medication washout, no treatment run-in, or other protocol-mandated intervention.
- Pre-existing medical conditions (other than the condition being studied) judged by the investigator to have worsened in severity or frequency or changed in character during the protocol-specified AE reporting period.
- Abnormal laboratory values or diagnostic test results constitute adverse events only if they induce clinical signs or symptoms or require treatment or further diagnostic tests.

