17.3. Statistical Analysis Plan

Demographic, baseline patient characteristics, and study outcomes are intended to be summarized graphically and numerically. Adverse events will be classified by type, incidence, severity and causality according to CTCAE v4.03. All adverse events will be summarized by patient, and all patients who received at least one cycle of the therapy (or discontinued due to treatment-related adverse event) will be included in the safety profile.

Continuous (e.g. age at on-study date) variables will be summarized using the 25th, 50th (median), and 75th percentiles, the range, as well as the mean and standard deviation. Categorical variables, (e.g. adverse events) will be reported as frequencies. 95% confidence intervals will be reported for all outcomes. The distribution of PFS and OS will be estimated using the Kaplan-Meier (product-limit) estimate with standard errors based on Greenwood's formula. No comparative statistical tests are planned for this study.

The Wilson 95% confidence intervals for 0 to 13 objective responses among 25 patients treated are listed in **Table 3**:

Table 3. Ninety-five percent (Wilson) confidence intervals for objective response rate among 25 patients.			
Number of Objective Responses	Objective Response Rate (%)	Lower Limit (%)	Upper Limit (%)
0	0	0	13.3
1	4	0.2	19.5
2	8	2.2	25.0
3	12	4.2	30.0
4	16	6.4	34.6
5	20	8.9	39.1
6	24	11.5	43.4
7	28	14.3	47.6
8	32	17.2	51.6
9	36	20.2	55.5
10	40	23.4	59.3
11	44	26.7	62.9
12	48	30.3	66.5
13	52	33.5	70.0

Considering the published data^{47,48} regarding the responses to standard of care chemotherapy regimens, we propose that observing the same or better clinical outcomes with avelumab monotherapy would warrant further therapeutic study in patients with advanced small intestinal adenocarcinoma.

Twenty-five patients will be enrolled on this clinical trial. We assume a one-sided type I error rate of 5% using a one-sample binomial test and desire 80% power to reject the null hypothesis that this regimen is ineffective if it elicits an objective response rate of 5%. Twenty-five patients provide 80% power to reject the null hypothesis if the true objective response rate (ORR) of this regimen is 21% or greater. This regimen will be considered sufficiently active to warrant further study in more definitive trials if 4 or more patients among 25 treated experience an objective response.

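### The adverse-event reporting period in 14.1 starts at first dose, which conflicts with the definition in 14.3.1 (biopsy complications count) and with the AE reviews scheduled before dosing in 7.1 to 7.3

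*Combined protocol and SAP*

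**What the plan says.** **Reporting period (14.1).** "Adverse events experienced by participants will be collected and reported from initiation of study medication", continuing to 30 days after the last dose. Events related to a study procedure or to study medication that are still ongoing at that point are followed further.

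**Definition (14.3.1).** The list of what counts as an adverse event includes "Complications that occur as a result of protocol-mandated interventions (e.g. invasive procedures such as biopsy" and, where applicable, "AEs that occur prior to assignment of study treatment associated with medication washout, no treatment run-in, or other protocol-mandated intervention".

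**Biopsy (7.1 and 8.7).** If archival tissue is not reasonably available, "the patient must be willing to undergo a fresh pre-treatment tumor biopsy". That requirement is waived if the lesion cannot be biopsied safely. In addition, under Note 8 of the Study Calendar, "an optional fresh biopsy will be requested from consenting subjects", including those who already have archival tissue. The calendar puts the fresh biopsy in the Screening column, and Section 7.2 introduces the screening list with "The following procedures must be completed ≤ 28 days prior" to first dose.

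**Adverse-event review before dosing (7.1 to 7.3).** The calendar marks adverse events at Screening, 7.2 lists them among the screening procedures, and 7.3 asks for a review on Cycle 1 Day 1 unless one was done in the preceding 7 days.

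**Safety analysis (17.3).** The safety profile includes "all patients who received at least one cycle of the therapy", plus those who discontinued because of a treatment-related adverse event.

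**The concern.** One part of the protocol defines a type of event as an adverse event, a second looks for it at a scheduled visit, and a third says that collecting and reporting have not yet begun. A site following 14.1 literally could find a bleed or perforation after a study biopsy and have no clear instruction to record it as an adverse event. Section 14.5.4 offers another place for it: a condition present before protocol treatment is medical history and becomes an adverse event only if it worsens.

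At stake is whether harm from a procedure done for the study is counted. Section 7.1 requires an excisional, incisional or core needle sample and rules out fine needle aspiration, so the procedure is invasive. If the complication keeps the patient from starting avelumab, it may appear in no summary at all.

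**Working it through.** There is no stated figure to reproduce. The check sets the sections side by side for a biopsy complication with onset between the biopsy and first dose, an interval of up to 28 days under the screening window.

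1. **Is it an adverse event?** Under 14.3.1, yes. Two other bullets in that list (newly emerging events and worsening pre-existing conditions) are restricted to the reporting period. The bullets on procedure complications and on pre-treatment events are not.

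2. **Is it inside the reporting period?** Under 14.1, no, because the period opens at first dose. Section 13.1 likewise makes patients evaluable for toxicity only from their first treatment.

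3. **Would anyone look for it?** Probably. Sections 7.1 to 7.3 schedule review at screening and around Cycle 1 Day 1. The second review may be done up to 7 days before first dose, and nothing requires the biopsy to come before it, so a late complication could still fall between reviews.

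4. **If serious, must it be reported?** Unclear. Section 14.5.13 requires all serious adverse events to be reported regardless of causality and gives no start date. It can be read as standing alone or as governed by the 14.1 period. The deaths rule in 14.5.3 is tied explicitly to the reporting period, although the opening of 14.1 refers to all deaths.

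5. **Does it reach the safety analysis?**
   - *Patient never dosed:* no. The patient has received no cycle and has not discontinued for a treatment-related event. Inclusion criterion 10 in 5.2 calls such a patient a pre-treatment screen failure.
   - *Patient later dosed:* undetermined. Section 17.3 summarises all adverse events of included patients and sets no onset cut-off, but what is available to summarise depends on what 14.1 let the site record.

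6. **A complication that begins or worsens after first dose** is inside the window under 14.1 and 14.3.1, so the gap concerns pre-dose onset only.

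**Size.** The documents give neither biopsy uptake nor complication rates. As pure illustration, suppose that 30% to 90% of 25 patients are biopsied and that 1% to 5% of those have a serious complication. The expected count is then 25 × 0.30 × 0.01 = 0.075 at the low end and 25 × 0.90 × 0.05 = 1.125 at the high end. Both ranges are assumptions. The count includes complications with onset after dosing, and the denominator of 25 leaves out consented patients who are never dosed. It should not be read as an estimate.

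**The case against.** The case on the other side is substantial, and it limits the point in four ways.

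**Collection.** From 14.1 alone, a reader might infer that nothing is collected before first dose. The documents do not support that, because 7.1, 7.2 and 7.3 all schedule adverse-event review earlier. What stands is that these sections contradict 14.1; they do not override it.

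**Serious events.** A reader might also infer that a serious biopsy complication would go unreported. That goes too far. Section 14.5.13 has no start date, 14.5.14 sends all adverse events to the IRB under institutional standards, and 14.1 asks for IRB notice of unanticipated events after a participant has stopped if they may reasonably be related to the study. These are plausible routes, but none says that it applies before first dose.

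**The safety result.** A reader might infer that the primary safety description is biased. It is not. The objective in 3.1 is the safety profile of avelumab monotherapy, and a complication that arises before the first infusion cannot be an effect of the drug. Nor is exclusion established for dosed patients. Section 17.4 adds that all patients included in the study must be assessed for safety, but it does not define included, so the never-dosed patient remains unsettled there and outside the profile in 17.3.

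**Exposure.** Archival tissue is enough for entry, the additional biopsy is optional, and patients with inaccessible lesions may enrol without one. It can also be argued that an optional biopsy is not protocol-mandated. Against that, 14.3.1 uses biopsy as its own example, and 4.3 plans exome sequencing of fresh-frozen pre-treatment biopsies with n=25, so the plan hopes for wide uptake.

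**Conclusion.** The inconsistency is real and narrow. The reporting period in 14.1 conflicts with the definition in 14.3.1 and with the pre-dose reviews in 7.1 to 7.3. By the wording of 14.1, a study-biopsy complication with onset before first dose is outside the reporting period. Whether a serious one is reportable is unclear. In 17.3, exclusion from the safety profile is certain only for patients never dosed; for dosed patients the section is silent on pre-dose events.

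The consequence is incomplete accounting for research-procedure harm, of unknown size. This conclusion rests on the wording alone and does not depend on any assumed rate. Severity is the lowest level.

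**What to change.** In 14.1, replace the single start date with two. Collect and report adverse events related to a study procedure, and all serious adverse events, from consent or from the first study-specific procedure. Collect all other adverse events from first dose. Refer to that rule in 14.5.13 so that serious-event reporting has a stated start.

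In 17.3, add a separate listing of pre-dose procedure-related events for all consented patients, whether or not they were dosed. Leave the summary of events after first dose as it is, so the description of avelumab's safety does not change.

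The cost is about one sentence and one listing, plus slightly more recording during screening. The screening and Cycle 1 Day 1 reviews that would supply the data are already in the schedule.

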14.2. Risks Associated with Avelumab

The PD-L1/PD-1 pathway is involved in peripheral tolerance; therefore, such therapy may increase the risk of immune-related adverse events, specifically the induction or enhancement of autoimmune conditions. AEs with potentially immune-related causes, including rash, hypothyroidism, hepatitis/transaminitis, colitis, myositis, and myasthenia gravis, have been observed in studies involving immunomodulators.

Although most immune-related AEs observed with immunomodulatory agents have been mild and self-limiting, such events should be recognized early and treated promptly to avoid potential major complications.

A more detailed safety profile of avelumab is provided in the avelumab Investigator's Brochure.

14.3. Safety Parameters and Definitions

14.3.1 Adverse Event (AE)

An AE is any unfavorable and unintended sign, symptom, or disease temporally associated with the use of an investigational medicinal product (IMP) or other protocol-imposed intervention, regardless of attribution. Progressive disease will not be considered an adverse event.

An adverse event includes the following:

- AEs not previously observed in the patient that emerge during the protocol-specified AE reporting period, including signs or symptoms that were not present prior to the AE reporting period.
- Complications that occur as a result of protocol-mandated interventions (e.g. invasive procedures such as biopsy).
- If applicable, AEs that occur prior to assignment of study treatment associated with medication washout, no treatment run-in, or other protocol-mandated intervention.
- Pre-existing medical conditions (other than the condition being studied) judged by the investigator to have worsened in severity or frequency or changed in character during the protocol-specified AE reporting period.
- Abnormal laboratory values or diagnostic test results constitute adverse events only if they induce clinical signs or symptoms or require treatment or further diagnostic tests.

14.3.2 Serious adverse event (SAE)

An AE should be classified as an SAE if the following criteria are met:

- It results in death.
- It is life threatening (i.e. the AE, in the view of the investigator, places the patient at immediate risk of death. It does not include an AE that, had it occurred in a more severe form, might have caused death.)
- It requires or prolongs inpatient hospitalization.

- It results in persistent or significant disability/incapacity (i.e. the AE results in substantial disruption of the patient's ability to conduct normal life functions).
- It results in a congenital anomaly/birth defect in a neonate/infant born to a mother exposed to the investigational product.
- It is considered a significant medical event by the investigator based on medical judgment (e.g. may jeopardize the patient or may require medical/surgical intervention to prevent one of the outcomes listed above).

Events not considered to be serious adverse events are hospitalizations for:

- Routine treatment or monitoring of the studied indication, not associated with any deterioration in condition, or for elective procedures.
- Elective or pre-planned treatment for a pre-existing condition that did not worsen.
- Emergency outpatient treatment for an event not fulfilling the serious criteria outlined above and not resulting in inpatient admission.
- Respite care.

14.4. Assessment of Adverse Events

All AEs and SAEs, whether volunteered by the patient, discovered by study personnel during questioning, or detected through physical examination, laboratory test, or other means, will be reported appropriately. Each reported AE or SAE will be described by its duration (i.e. start and end dates), regulatory seriousness criteria if applicable, suspected relationship to the study drug (see following guidance), and actions taken.

To ensure consistency of AE and SAE causality assessments, investigators should apply the following general guidelines:

Yes

There is a plausible temporal relationship between the onset of the AE and administration of avelumab, and the AE cannot be readily explained by the patient's clinical state, intercurrent illness, or concomitant therapies; and/or the AE follows a known pattern of response to avelumab; and/or the AE abates or resolves upon discontinuation of avelumab or dose reduction and, if applicable, reappears upon re-challenge.

No

Evidence exists that the AE has an etiology other than avelumab (e.g. pre-existing medical condition, underlying disease, intercurrent illness, or concomitant medication); and/or the AE has no plausible temporal relationship to avelumab administration (e.g. cancer diagnosed 2 days after first dose of study drug).

